Study sites and number of subjects planned

The study will be conducted at approximately 30 sites in the United States. It is estimated that approximately 750 patients will be enrolled during a recruitment period of approximately 6-12 months. Each participant will be followed through 28 days or hospital discharge, whichever comes first.

Study Initiation	Phase of development
Estimated date of first subject enrolled	Q2 2020

Study Design

This is a multicenter, open-label, 2x2 factorial, randomized-controlled trial in critically-ill patients with novel coronavirus disease 2019 (COVID-19) evaluating the efficacy and safety of full-dose vs. standard prophylactic dose anticoagulation and of antiplatelet vs. no antiplatelet therapy for prevention of venous and arterial thrombotic events. The trial will follow the principles of a prospective randomized open blinded end-point (PROBE) design.

Study Objectives

Primary Efficacy Objective:	Primary Efficacy Outcome Measure:
To assess the efficacy of: 1) full-dose anticoagulation (FDAC) versus standard-dose prophylactic anticoagulation (SDPAC) and 2) antiplatelet (AP) therapy versus no AP therapy on venous or arterial thrombotic events in critically-ill patients with COVID-19.	The hierarchical composite endpoint of: 1. Death due to venous or arterial thrombosis 2. Pulmonary embolism 3. Clinically evident deep venous thrombosis (DVT) 4. Type 1 myocardial infarction (MI) 5. Ischemic stroke 6. Systemic embolic event (SEE) or acute limb ischemia (ALI) 7. Clinically silent DVT

Key Secondary Efficacy Objective:	Key Secondary Efficacy Outcome Measure:
To assess the efficacy of: 1) FDAC versus SDPAC and 2) AP therapy versus no AP therapy on clinically evident venous or arterial thrombotic events in critically-ill patients with COVID-19.	The hierarchical composite endpoint of: 1. Death due to venous or arterial thrombosis 2. Pulmonary embolism 3. Clinically evident DVT 4. Type 1 MI 5. Ischemic stroke 6. SEE or ALI

Primary Safety Objective:	Primary Safety Outcome Measure:
To evaluate the safety of: 1) FDAC versus SDPAC and 2) AP therapy versus no AP therapy in critically-ill patients with COVID-19.	Composite endpoint of fatal or life-threatening bleeding

Target Population

Patients with COVID-19 requiring intensive care unit (ICU) admission (critically-ill) without an indication for full-dose anticoagulation.

Inclusion Criteria (See Section 6 for additional details)

Patients must meet all the following criteria to be eligible for enrollment:

1. Age ≥ 18 years (male or female)
2. Acute infection with severe acute respiratory syndrome coronavirus 2 (SARS-CoV2)
3. Currently admitted to an ICU

Key Exclusion Criteria (See Section 6 for complete listing)

1. Ongoing or planned full-dose (therapeutic) anticoagulation for any indication
2. Ongoing or planned treatment with dual antiplatelet therapy
3. Contraindication to antithrombotic therapy or high risk of bleeding

Investigational Product, Dosage, and Mode of Administration

Acceptable initial regimens for full-dose anticoagulation:

- Unfractionated heparin (UFH) administered intravenously with a nomogram targeting an aPTT of 1.5-2.5 times the control as per institutional therapeutic target for treatment of VTE
- Enoxaparin 1 mg/kg administered subcutaneously (SC) every 12 hours

Antiplatelet:

- Clopidogrel 300 mg administered once orally on the day of randomization, followed by 75 mg administered orally once daily on subsequent days

Comparator Product, Dosage, and Mode of Administration

Acceptable initial regimens for standard dose prophylactic anticoagulation:

- Enoxaparin 40 mg administered SC once daily (reduce to 30 mg if CrCl < 30 ml/min)*
- Heparin 5,000 units administered SC three times daily

*Enoxaparin 30-40 mg administered SC twice daily may also be considered if CrCl ≥ 30 ml/min and BMI ≥ 35 kg/m².

Antiplatelet:

- None

Statistical Methods

The primary efficacy assessments will involve on-treatment (OT) comparisons of the effect of 1) full-dose anticoagulation (FDAC) versus standard-dose prophylactic anticoagulation (SDPAC) (pooled across antiplatelet regimens) and 2) antiplatelet (AP) versus no AP therapy (pooled across anticoagulant regimens) on the composite endpoint of death due to venous or arterial thrombosis, pulmonary embolism, clinically evident DVT, type 1 MI, ischemic stroke, SEE or ALI, or clinically silent DVT through the follow-up period. Intention-to-treat (ITT) comparisons will also be performed as additional analyses.

The primary analysis will be conducted by estimating the unmatched win ratio evaluating the composite in a hierarchical manner. A win ratio greater than 1 will be in favor of the FDAC arm and AP arm, respectively. In a secondary analysis of the primary composite endpoint, clinical event rates will be calculated using the time to first event according to the cumulative incidence function. Differences in clinical outcomes between the two treatment groups will be assessed using the Gray's test for equality of cumulative incidence functions.

With a 2-sided alpha of 0.05, a 40% event rate in the group receiving both SDPAC and no AP therapy at a median follow-up of 14 days, a 10% competing risk of mortality, and a 1% dropout rate, approximately 750 patients would provide approximately 170 events and therefore at least 80% power to detect a hazard ratio of 0.65 using Gray's test for equality of cumulative incidence function. This approach is expected to be conservative with respect to the primary efficacy analysis, for which greater power is expected using the win-ratio analysis.

3. Study Background & Rationale

In addition to respiratory insufficiency, patients with coronavirus disease (COVID)-19, the disease caused by the severe acute respiratory syndrome coronavirus-2 (SARS-CoV2), have a range of serious cardiovascular (CV) complications¹⁻⁴, including venous and arterial thrombotic events.⁵⁻⁸ Thrombotic event rates are believed to be substantially higher in patients requiring ICU-level care, among whom it is suggested that up to 2/3 may develop clinically evident or clinically silent venous thrombotic complications despite standard doses of thromboprophylaxis.⁶⁻⁸ While an accurate estimate of the rate of arterial thrombotic events is unknown at this time, case reports describe acute arterial thrombotic events, including ischemic strokes, acute coronary syndromes and ischemic limb events.^{5, 9, 10} Proposed mechanisms for the increased thrombotic risk in patients with COVID-19 include excessive inflammation and immobilization in the setting of aberrant coagulation parameters and diffuse intravascular coagulation (DIC).^{11, 12} In addition, early autopsy series have been notable for the presence of megakaryocytes in affected organs, suggesting that platelet aggregation and platelet-rich clot formation may be important pathogenetic mechanisms.¹³

The benefit of thromboprophylaxis with low-dose anticoagulation for the prevention of venous thromboembolism (VTE) in acutely-ill hospitalized medical patients is well-established.¹⁴ Moreover, in patients at very high risk for VTE (e.g., patients with a history of unprovoked VTE), thromboprophylaxis with full-dose anticoagulation has been shown to be more effective than low-dose anticoagulation in preventing thrombotic events.¹⁵ Given the apparent very high risk of venous thrombotic complications in patients with severe COVID-19, FDAC may be a more effective thromboprophylaxis strategy than SDPAC, but may be associated with an increased risk of bleeding. The safety of this strategy in patients with COVID-19 has not yet been adequately studied.

Antiplatelet therapy is recommended for prevention of arterial thrombotic events in high-risk patient populations.¹⁶⁻¹⁸ Antiplatelet therapy has also demonstrated benefit for prevention of new and recurrent VTE in high-risk patient populations.¹⁹⁻²¹ The thienopyridine clopidogrel is superior to aspirin for prevention of atherothrombotic events with a similar safety profile and may be associated with less GI bleeding.²² Thus, it is reasonable to hypothesize that in critically-ill patients with COVID-19, addition of antiplatelet therapy with clopidogrel may reduce the incidence of arterial and venous thrombotic events with an acceptable safety profile. However, the balance of safety (bleeding) and efficacy of this approach merits rigorous investigation.

The study described here, COVID-PACT, is a multicenter, open-label, 2x2 factorial, randomized-controlled trial evaluating the safety and efficacy of antithrombotic therapy (anticoagulation and antiplatelet) versus standard of care for prevention of venous and arterial thrombotic events in critically-ill patients with COVID-19.

4. Study Objectives

The primary objectives of this study are to assess the effect of:

1. FDAC as compared with SDPAC, and
2. AP therapy compared with no AP therapy,

on the clinical outcomes of venous and arterial thrombotic events in critically-ill patients with COVID-19.

The key safety objectives are to assess the safety of:

[figure not shown]
1. FDAC as compared with SDPAC, and
2. AP therapy compared with no AP therapy,

with respect to incidence of fatal or life-threatening bleeding.

See Section 8 (Study Outcomes) for additional secondary and exploratory objectives.

5. Study Design

This is a phase 4, multicenter, open-label, 2x2 factorial, randomized-controlled trial using a PROBE design. The trial will be conducted in approximately 30 sites in the United States. Approximately 750 patients will be enrolled. Patients will be randomized in a 1:1 allocation ratio to receive either FDAC or SDPAC. In patients without an ongoing indication for AP therapy at baseline, a second randomization will be performed in a 1:1 allocation ratio to either AP or no AP therapy. Randomization to FDAC vs. SDPAC will be stratified by whether or not the patient is planned to receive non-study AP therapy and therefore would not qualify for randomization in the second factorial treatment comparison. Patients will be assessed clinically and with bilateral lower extremity venous ultrasound between 10 and 14 days post-randomization. Patients will be followed through hospital discharge or 28 days, whichever occurs first, for a maximum follow-up of 28 days. The anticipated total duration of the study is 6-12 months.

6. Study Population

Inclusion Criteria

Patients must meet all the following criteria to be eligible for enrollment:

1. Age \geq 18 years (male or female)
2. Acute infection with severe acute respiratory syndrome coronavirus 2 (SARS-CoV2)*
3. Currently admitted to an intensive care unit (ICU)**

**Acute SARS-CoV2 infection is defined as a documented, positive SARS-CoV2 RT-PCR, SARS-CoV2 IgM antibody test, or other accepted assay (see Manual of Site Operations) with active respiratory signs or symptoms during the current hospitalization.*

***Where ICU admission occurred \leq 96 hours prior to randomization. ICU admission also includes patients requiring ICU-level care in other units. Criteria for ICU-level of care are defined in the Protocol Appendix.*

Exclusion Criteria

Patients who meet any of the following criteria are excluded from the study:

1. Ongoing (>48 hours) or planned full-dose (therapeutic) anticoagulation for any indication
2. Ongoing or planned treatment with dual antiplatelet therapy
3. Contraindication to antithrombotic therapy or high risk of bleeding due to conditions including, but not limited to, any of the following:
 - a) History of intracranial hemorrhage, known CNS tumor or CNS vascular abnormality
 - b) Active or recent major bleeding within the past 30 days with untreated source
 - c) Platelet count $<$ 70,000 or known functional platelet disorder
 - d) Fibrinogen $<$ 200 mg/dL
 - e) International normalized ratio (INR) $>$ 1.9
4. History of heparin-induced thrombocytopenia
5. Ischemic stroke within the past 2 weeks
6. Pregnancy
7. Study staff or their family members
8. Any condition which in the investigator's assessment might increase the risk to the patient or decrease the chance of obtaining satisfactory data to achieve the objectives of the study
9. Subjects for whom further care is being forgone at the decision of the subject, family, and/or treating team ("comfort measures only")

Exclusion-based laboratory results are based on most recent values from within 2 days prior to randomization for platelet count and INR and within 3 days prior to randomization for fibrinogen.

Patients who meet the following criterion are excluded from the second randomization (antiplatelet therapy vs. no antiplatelet therapy):

1. Ongoing or planned antiplatelet therapy, including aspirin monotherapy

7. Study Intervention

7.1 Investigational Product Information:

Acceptable initial regimens for FDAC include the following:

- UFH administered intravenously with a nomogram targeting an aPTT of 1.5-2.5 times the control as per institutional therapeutic target for treatment of VTE
- Enoxaparin 1 mg/kg administered subcutaneously every 12 hours (if CrCl \geq 30 ml/min)

Acceptable initial regimens for SDPAC include the following:

- Enoxaparin 40 mg administered subcutaneously once daily (if CrCl \geq 30 ml/min)*
- Enoxaparin 30 mg administered subcutaneously once daily (if CrCl $<$ 30 ml/min)
- Heparin 5,000 units administered subcutaneous three times daily

**Enoxaparin 30-40 mg administered SC twice daily may also be considered if CrCl \geq 30 ml/min and BMI \geq 35 kg/m².*

Acceptable regimen for randomized antiplatelet therapy is:

- Clopidogrel 300 mg administered once orally on the day of randomization, followed by 75 mg administered once daily on subsequent days

7.2 Randomized Treatment Assignment: Randomization to FDAC versus SDPAC and AP therapy versus no AP therapy will be done via an Interactive Web-based Randomization System (IWRS). Treatment will be open-label and hospital-supplied by the institutional pharmacy per standard practice using local, standard formulations, concentrations and titration.

Randomization and study treatment initiation should be done as soon as possible following ICU admission or the requirement for ICU-level of care and no longer than 96 hours after meeting ICU-level criteria.

7.3 Duration of Randomized Treatment: The study allocated regimen should be continued until hospital discharge (including after ICU discharge) or through 28 days post-randomization, whichever occurs first.

7.4 Transition in Randomized Treatment Assignment: The investigator may transition between acceptable regimens within the randomized treatment assignment as deemed appropriate clinically (e.g., transition from enoxaparin to subcutaneous heparin for SDPAC in the setting of new or worsening renal failure). Transitions to direct thrombin inhibitors, or fondaparinux are permitted if heparin-induced thrombocytopenia is confirmed or suspected. After a patient is transferred out of the ICU, transitions to oral anticoagulation are also permitted in the absence of significant renal or hepatic dysfunction (see Protocol Appendix for further details). Transitions in anticoagulant therapy will be recorded in the

eCRF. Refer to the Appendix for further guidelines regarding transitions in randomized treatment assignment including acceptable alternative regimens.

7.5 Blinding: Treatment will be open-label without blinding.

7.6 Concomitant Medications: All non-antithrombotic therapy is at the discretion of the patient's treating physicians. Non-study anticoagulant or antiplatelet therapy is not permitted while receiving the study allocated regimen unless there is a change in the patient's clinical status requiring an alternative regimen.

7.7 Discontinuation of Study Drug: Patients and healthcare providers may voluntarily discontinue study drug for any reason at any time. If adverse events occur that are believed to be due to study drug, or safety events occur that, in the opinion of the investigator, contraindicate further dosing of study drug, study drug may be temporarily interrupted or permanently discontinued. Whenever possible, restarting study drug should be encouraged, so long as the investigator judges that the potential benefit outweighs the risk. Situations that warrant temporary or permanent study drug discontinuation include:

- Active clinically significant bleeding
- Acute hemorrhagic or ischemic stroke at meaningful risk for hemorrhagic transformation
- Severe thrombocytopenia (platelet count <50,000)
- Evidence of overt disseminated intravascular coagulation (e.g. fibrinogen levels <150 mg/dl or INR >2.9 despite adequate vitamin K repletion). See Manual of Site Operations for guidelines to help discriminate DIC from sepsis induced coagulopathy.
- Need for invasive procedures requiring extended interruption of antithrombotic therapy

The investigator should contact the TIMI Hotline with any questions regarding study drug discontinuation and must update the eCRF with any study drug discontinuation and record it in the eCRF. Discontinuation of study drug does not mean discontinuation of follow-up. All study assessments should be continued even if study drug is discontinued.

In the course of the patient's participation, use of the alternative antithrombotic strategy (crossover) may be deemed clinically indicated due to a change in the patient's clinical status. Examples include: 1) a patient randomized to standard-dose prophylactic anticoagulation develops atrial fibrillation or deep venous thrombosis, requiring full-dose anticoagulation; or 2) a patient randomized to no antiplatelet therapy experiences an acute coronary syndrome requiring addition of an antiplatelet agent. The crossover in therapy will be recorded in the eCRF.

7.8 Withdrawal of Consent: Patients are free to completely withdraw from the study at any time (which means permanent discontinuation of IP and all follow-up assessments) without prejudice to further treatment. Withdrawal of consent should only occur if the patient refuses any further assessments or contact whatsoever. Patients who do not want in-person follow-up after cessation of IP should be offered alternative methods of follow-up including assessment of health status via treating physicians or medical records. Such patients would then not be viewed as withdrawals of consent. The investigator must explain to the patient all options for continued participation, and document which options were refused by the patient and the reason for refusal. Withdrawal of consent must be ascertained and documented in writing by the site investigator who must inform the TIMI Hotline and document the withdrawal of consent in the eCRF and medical records. Patients will be asked about the reason(s) for withdrawal of consent.

8. Study Outcomes

Efficacy Outcomes

Primary Efficacy Outcome

The hierarchical composite endpoint of:

1. Death due to venous or arterial thrombosis
2. Pulmonary embolism
3. Clinically evident DVT
4. Type 1 MI
5. Ischemic stroke
6. Systemic embolic event (SEE) or acute limb ischemia (ALI)
7. Clinically silent DVT

Key Secondary Efficacy Outcome

The hierarchical composite endpoint of:

1. Death due to venous or arterial thrombosis
2. Pulmonary embolism
3. Clinically evident DVT
4. Type 1 MI
5. Ischemic stroke
6. SEE or ALI

Secondary Efficacy Outcomes

- Composite of venous thrombotic events (PE or clinically evident or silent DVT)
- Composite of arterial thrombotic events (ischemic stroke, SEE or ALI, or T1MI)
- Each of the individual components of the primary efficacy outcome
- Cardiovascular death

Exploratory Efficacy Outcomes

- Clinical improvement on COVID ordinal scale recommended by WHO R&D Blueprint Group
- Ventilator-free days (at 28 days post-randomization)
- Time from ICU admission to ICU discharge
- Acute kidney injury
- Need for new renal replacement therapy
- Pulseless electrical activity cardiac arrest
- Catheter thrombosis
- Myocardial dysfunction
- All-cause mortality

Safety Outcomes

Primary Safety Outcome

Time to first occurrence of fatal or life-threatening bleeding

Secondary Safety Outcome

- GUSTO moderate or severe bleeding

9. Study Procedures

Screening and Randomization

- Obtain written informed consent from patient or legal authorized representative
- Review inclusion/exclusion criteria (including pregnancy testing for women of child bearing potential), relevant medical history, vital signs (including weight), and medications
- Review or obtain labs (platelet count, INR and fibrinogen)
- Randomize (Day 0) using the Interactive Web Randomization System (IWRS)
- Initiate randomized anticoagulant strategy and, if applicable, antiplatelet therapy

Follow-up (through day 28 or hospital discharge, whichever occurs first)

- Continue randomized antithrombotic therapy
- Monitor anticoagulation as per local practice; obtain INR daily and fibrinogen at least every 3 days while receiving ICU-level care (see Appendix for details)
- Obtain bilateral lower extremity venous ultrasound as a single assessment any time between days 10-14. If a patient crosses over or discontinues randomized anticoagulation strategy on Day 4 through Day 9, this assessment should be performed as close to the date of discontinuation as possible (and no longer than 3 days after discontinuation). For crossover or permanent discontinuation prior to Day 4, this assessment is not required.
- Assess for efficacy and safety events

Additional details about study operations can be found in the Manual of Site Operations

10. Site Training and Monitoring

10.1 Training of Study Site Personnel: Before enrolling patients into the study, the requirements of the Clinical Study Protocol and related documents will be reviewed with the investigational staff who will be trained in any study-specific procedures. The site principal investigators will ensure that appropriate training relevant to the study is given to all staff, and that any new information relevant to the performance of this study is forwarded to the staff involved. The site principal investigator will also maintain a record of all individuals involved in the study.

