11.1 Analysis Sets

- a) The On-Treatment Analysis Set will consist of all randomized patients who received at least one dose of study drug. However, only those events/observations occurring during therapy with the randomized treatment strategy or within 3 days of the last dose of randomized treatment will be a part of this analysis set. A transition in randomized treatment as defined in Section 7.4 is not considered a deviation in therapeutic strategy and observations occurring after the transition will be a part of this analysis set. Crossovers and permanent discontinuations (Section 7.7) of randomized treatment are considered an end to the randomized anticoagulant or antiplatelet therapeutic strategy; only observations occurring up to 3 days after crossovers or discontinuations of randomized treatment will be a part of this analysis set. The primary assessment for efficacy outcomes will be analyzed based on the On-Treatment Analysis Set.
- b) The Intention-to-Treat Analysis Set will consist of all randomized patients with the exception of those who did not qualify for randomization and did not receive study drug but were inadvertently randomized into the study. Following the intention-to-treat

principle, patients will be analyzed according to the treatment group to which they were assigned at randomization. Additional assessments for efficacy outcomes will be analyzed based on the Intention-to-Treat Analysis Set.

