11.2 Analyses

The primary efficacy analysis will be performed using the On-Treatment Analysis Set. The primary efficacy assessments will involve on-treatment comparisons of the effect of allocation to: 1) FDAC versus SDPAC (pooled across AP regimens); and 2) AP therapy versus no AP therapy (pooled across anticoagulation regimens) on the primary composite endpoint of death due to venous or arterial thrombosis, pulmonary embolism, clinically evident DVT, type 1 MI, ischemic stroke, SEE or ALI, or clinically silent DVT through the follow-up period. Clinical event rates will be calculated according to the cumulative incidence function. Intention-to-treat comparisons will also be performed as additional analyses.

The primary analysis will be conducted by estimating the unmatched win ratio by comparing 1) every participant in the FDAC arm to every participant in the SDPAC arm to determine a winner, and 2) every participant in the AP therapy to every participant in the no AP therapy arm to determine a winner. The estimated win ratio (the total number of wins in the FDAC arm divided by the total number of wins in the SDPAC arm, and the total number of wins in the AP therapy arm divided by the total number of wins in the no antiplatelet therapy arm) will be calculated evaluating the composite in a hierarchical manner. A win ratio greater than 1 will be in favor of the FDAC arm and AP therapy arm, respectively.

The corresponding two-sided 95% confidence intervals will be calculated. The analysis will be performed using the unmatched pair win ratio approach.²³ For the comparison of FDAC vs. SDPAC, the analysis will be stratified by ongoing or planned AP therapy and the second factorial treatment comparison of AP therapy vs. no AP therapy for those eligible. For the analysis of AP therapy vs. no AP therapy, the analysis will be stratified by FDAC vs. SDPAC randomization. Contributions of each component of the composite endpoint to total number of winners used in estimation of the win ratio will be reported.

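### Does a clopidogrel-only stop, which does not bring the ultrasound forward, bias the primary antiplatelet comparison?

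*Combined protocol and SAP*

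**What the plan says.** Section 9 (Follow-up) schedules one bilateral leg ultrasound between Days 10 and 14. Its early-scan rule names one strategy only: "If a patient crosses over or discontinues randomized anticoagulation strategy on Day 4 through Day 9, this assessment should be performed" as near the stop as possible, and at most 3 days after it. For stops or crossovers before Day 4 no scan is required.

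Section 11.1(a) treats both strategies alike. Crossovers and permanent discontinuations "are considered an end to the randomized anticoagulant or antiplatelet therapeutic strategy", and "only observations occurring up to 3 days after crossovers or discontinuations of randomized treatment will be a part of this analysis set". This on-treatment set carries the primary efficacy analysis.

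Section 7.7 keeps patients under observation after a stop: "All study assessments should be continued even if study drug is discontinued". It also says of interruptions: "Whenever possible, restarting study drug should be encouraged". Its example of leaving the no-AP strategy is that "a patient randomized to no antiplatelet therapy experiences an acute coronary syndrome requiring addition of an antiplatelet agent".

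Section 11.2 compares "every participant in the AP therapy to every participant in the no AP therapy arm to determine a winner", stratified by anticoagulant allocation. It does not describe how a pair is scored when the two on-treatment windows close on different days, and it refers further analytic detail to the SAP. It adds: "Intention-to-treat comparisons will also be performed as additional analyses".

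**The concern.** The 3-day limit on the early scan matches the 3-day tail of the on-treatment window, so the rule looks designed to keep the scan inside the window. The antiplatelet strategy has no counterpart. A patient who stops clopidogrel for good but stays on the assigned anticoagulant is scanned on Days 10-14 as usual, and that scan may then fall outside the primary AP analysis.

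The loss need not be balanced. An AP patient can stop a drug, whereas a no-AP patient can leave the assigned strategy only by crossing over. Treatment is open-label. If an analyst scored a patient with a closed window as free of silent DVT, AP patients would win pairs they had not earned, in one of the trial's two primary comparisons.

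**Working it through.** **The plan's event figure.** For a hazard ratio of 0.65, two-sided alpha 0.05, 80% power and 1:1 allocation, 4 × (1.960 + 0.842)² / (ln 0.65)² = 169.2, so 170 events, as Section 11.5 states. The present point does not depend on it; 170/750 = 22.7% is used below as the overall event rate.

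**Which scans are lost.** A stop on day s closes the window on day s + 3. A scan on day t (10 to 14) is lost if t > s + 3.

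| Stop day | Window closes | Scan days lost (of 5) |
|---|---|---|
| 4, 5, 6 | 7, 8, 9 | 5 each |
| 7 | 10 | 4 |
| 8 | 11 | 3 |
| 9 | 12 | 2 |
| 10 | 13 | 1 |
| 11 or later | 14 or later | 0 |

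With stops even over Days 4-10 and scans even over Days 10-14, (15 + 4 + 3 + 2 + 1)/35 = 25/35 = 71% are lost. Section 11.1(a) refers both to the last dose and to the discontinuation. If the window runs from a last dose taken the day before the stop, Day 7 always loses the scan, Days 8-11 sometimes do, and the share over Days 4-10 is (20 + 4 + 3 + 2)/35 = 29/35 = 83%.

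**How many scans.** Section 11.5 assumes 10% are not eligible for the AP randomization: 750 × 0.9 = 675, about 337 per arm. Suppose 10% of the AP arm (34 patients) stop only clopidogrel on Days 4-10; this rate is an assumption. Then 34 × 25/35 = 24, or 34 × 29/35 = 28, would lose the scan if all stayed in hospital. These are averages for evenly spread stops; if every stop fell on Days 4-6, all 34 would be lost.

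Some patients leave before the scan. With an exponential stay of median 14 days (an assumption borrowed from the synopsis follow-up figure), a patient in hospital on day s is still there on day t with probability 2^(−(t−s)/14). Averaged over the lost combinations this is 0.74, or 0.76 under the last-dose reading. That gives 24.3 × 0.74 = 18 and 28.2 × 0.76 = 21 scans.

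**Effect on the win ratio.** Simulated with no true effect, 22.7% event rate, half of events silent, and no no-AP crossovers. Stopping is unrelated to risk in the first three rows, at 5/10/14% of AP patients.

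| Scoring | Null win ratio | Two-sided error |
|---|---|---|
| Lost scan counted event-free | 1.02 / 1.04 / 1.05 | 5.1 / 5.5 / 6.2% |
| Whole closed window counted event-free | 1.03 / 1.06 / 1.08 | 5.1 / 6.3 / 7.3% |
| Shared on-treatment follow-up (range over all 24 settings) | 0.997-1.002 | 4.7-5.4% |
| Event-free scoring, risk-related stopping, 14% stopping | 1.10 (scan) and 1.15 (window) | 8.4% and 12.5% |

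The Monte Carlo band around 5% is 4.6-5.4%. With half as many no-AP crossovers as AP stops, still unrelated to risk, even event-free scoring stays inside that band (win ratio at most 1.04). Full follow-up of the same data, as in intention-to-treat, gives 0.996-1.003 and 4.7-5.6%.

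**The case for a change.** The strongest case for acting is that the choice of scoring can move a primary result. At 14% stopping with no crossovers, counting whole closed windows as event-free raises false wins for AP from the nominal 2.5% to 6.3%. At a 33% event rate the two-sided error reaches 9.0%. If stopping tracks thrombotic risk, even shared follow-up leaves a null win ratio of 1.01-1.05 with 4.9-6.0% error. A sentence in Section 11.2 costs nothing.

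The day arithmetic stands, and so does the remark that Section 11.2 is silent on pair scoring. The step from there to bias does not follow. Section 11.1(a) admits only in-window observations to the set; that reads naturally as follow-up ending when the window closes, not as continued follow-up without events. The larger errors need high stopping, few or no crossovers and event-free scoring together, and the largest also need an assumed dependence of stopping on risk. Several of the listed reasons for stopping, such as active bleeding or severe thrombocytopenia, apply to study drug generally; where both drugs stop on Days 4-9, the early scan is triggered.

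The possible remedies gain little:

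- **Tie rule.** Tying every pair on silent DVT unless both patients have an in-window scan, with censoring at discharge, cuts simulated power for a 35% reduction from 75.8% to 65.6%. Section 11.5 expects only about 70% for this comparison.
- **Supportive analysis.** Counting the scan and all events up to it, regardless of stopping, comes close to the intention-to-treat analysis already planned, with lower simulated power (70.8%).
- **Moving the scan.** An earlier scan after a clopidogrel-only stop would shorten silent-DVT ascertainment in the anticoagulation comparison, which uses the same scan.

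The first two would not return the lost scans to the primary analysis.

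**Conclusion.** The early-scan rule and the on-treatment window do not match for antiplatelet-only stops. The consequence is a modest loss of silent-DVT data in one comparison: about 18 to 21 scans for each 34 evenly spread stoppers, given the assumed length of stay. No-AP crossovers on the same days lose their scans too, which offsets part of any imbalance. The six higher tiers do not rest on the scan, the key secondary outcome omits silent DVT, and intention-to-treat retains the scans.

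Material bias requires a scoring convention the protocol does not state and that fits Section 11.1(a) poorly. With the ordinary convention of comparing pairs over shared follow-up, bias is negligible if stopping is unrelated to risk and small (1.01-1.05) under the risk-related settings simulated. An analyst would fill this gap sensibly in the SAP. Keeping one scan date for patients who remain on their anticoagulant strategy is also a fair trade-off. No change to the plan is called for. This conclusion rests on assumed stop rates and silent-DVT shares, and on SAP scoring that follows the on-treatment definition as written.
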